9.2. Setting

9.2.1. Source population

The source population includes US adults age 65 and older who are enrolled in Medicare any time from 2017 through 2021. Medicare is fully funded by the US government to subsidize healthcare services for individuals aged 65 and older or who are entitled because of a qualifying condition other than age. CMS is the US federal agency responsible for oversight and management of the Medicare program. As defined by CMS, Medicare is a health insurance program for:

- 1. People age 65 and older
- 2. People under age 65 years old with certain disabilities
- 3. People of all ages with End-Stage Renal Disease (ESRD)

Most US adults in the Medicare program (80%) qualify based on age 65 years and older and about 20% are younger than 65 years old and qualify due to a disabling condition. Approximately 55%-67% of the Medicare population is covered fully or partly through a fee-for-service arrangement as opposed to a supplemental Medicare Advantage plan (see below).

Individuals enrolled in Medicare receive benefits from different 'parts' of Medicare insurance that pay for all or a portion of specific healthcare services. These parts are referred to as Parts A, B, C and D. Each is described below.

- Medicare Part A: Also referred to as Hospital Insurance, Part A pays for healthcare services provided in inpatient settings including hospitals, critical access hospitals, skilled nursing facilities (SNFs) (not custodial or long-term care), hospice care and some home health care.
- Medicare Part B: Also referred to as Medical Insurance, Part B pays for doctors' services and outpatient care as well as services not covered by Part A, such as physical and occupational therapists and some home health care. Certain vaccines are covered under Part B: influenza, pneumococcal, and Hepatitis B.
- Medicare Part C: Also referred to as supplemental coverage, Part C was first established in 1997 under the name Medicare + Choice but was renamed in 2003 to the Medicare Advantage program. Under Part C, CMS contracts with public or private organizations to offer a variety of health plan options for Medicare beneficiaries, such as health maintenance organizations, provider sponsored associations, and preferred provider organizations. These health plans must provide all Medicare Parts A and B benefits, and most offer additional benefits beyond those covered under the original Medicare program. Individuals pay a monthly premium for Part C. Services provided under Part C are not available in the CMS CCW Medicare database, and so all data will be missing for individuals who are only enrolled in Part C during the study period.
- Medicare Part D: Also referred to as Prescription Drug Coverage, Part D first became available in January 2006. It is available to everyone with Medicare, but

individuals must enroll in a Medicare-approved plan that offers Medicare drug coverage. Individuals must pay a monthly premium to receive Part D benefits.

9.2.2. Study population (Amended 15 July 2022)

The study population will be comprised of all US Medicare beneficiaries who received the RZV vaccine (i.e., exposed) in 2018 through 2020 as well as a random sample of Medicare beneficiaries who did not receive the RZV vaccine but who had at least one preventive care visit (*i.e., comparator group*), as defined in Section 9.7.5. The study population is a longitudinal cohort that is followed over time until they are no longer in Medicare. This means there will be continuity of their data over time, i.e., there is not a new random sample selected each study year.

Study inclusion / exclusion criteria

US Medicare beneficiaries who meet the following criteria will be included in the study:

- 1. Age 65 and older at the date of the RZV vaccination or preventive care visit for the RZV unvaccinated comparator, **AND**
- 2. Enrolled in Medicare due to age or ESRD as the original and current qualifying reason, **AND**
- 3. Continuously enrolled in Medicare Parts A, B, and D fee-for-service for at least 365 days preceding the date of RZV vaccination or preventive care visit for the RZV unvaccinated comparator. Continuous *enrollment* is determined by Medicare enrollment in the month of the RZV vaccination or preventative care visit and *enrollment* in at least 11 of the 12 preceding months.

Beneficiaries enrolled due to ESRD or receiving dialysis are included in the study population as this condition is prevalent among US Medicare beneficiaries aged 65 and older, and this is a subgroup in which RZV use may be common. The requirement for continuous enrollment in Medicare Parts A, B, and D in the 365 days, *allowing one calendar month gap*, before the RZV vaccination or preventive care visit will ensure complete data on all services covered by Medicare on a fee-for-service basis in the baseline study period for the cohort design. Parts A and B provide information on the HOI and Part D provides information on RZV exposure.

Beneficiaries who satisfy the following criteria will be excluded:

- 1. Continuously enrolled only in Medicare Part C in the baseline period, OR
- 2. Enrolled in Medicare due to disability as the original qualifying reason for enrollment.

Individuals who qualify for Medicare due to a disability are likely not comparable to the population of adults age 65 and older within the Medicare health insurance program in many important aspects, such as medical comorbidities, illness severity, and health seeking behavior.

It will be possible to obtain sufficient sample sizes for all HOIs with a study population accrual from 2018 through 2020. Conservative estimates are that 1.5 million Medicare beneficiaries with Parts A, B, and D will receive RZV in each year from 2018 through 2020, for a total RZV exposed of 4.5 million across all three years. If 50% are enrolled in Parts A, B, and D for at least 365 days, there will be a little more than 2 million individuals exposed to RZV who meet the study criteria. It will be possible to accrue 8 million unvaccinated individuals with a preventive care visit in 2018 through 2020 to achieve a 1:4 ratio of exposed to comparators for the cohort design.

All CMS CCW Medicare claims data from January 2017 through December 2021 will be obtained for the RZV exposed and the unvaccinated comparators accrued from 2018 through 2020. Data spanning five years are needed to cover a) the 365 days prior to the HOI for the SCRI design; b) the 365 days prior to the index date for the cohort design; c) the 60- and 84-day risk and control intervals for the SCRI design; and d) the 183-day risk window for the cohort design.

9.3. Variables

9.3.1. Exposure measure

RZV exposure will be defined as receipt of at least one dose of RZV for the primary analyses; per-dose analyses will be performed in secondary analyses. RZV vaccination will be identified by means of the national drug code (NDC) and by the Current Procedural Terminology (CPT) code. Part D generally pays for commercially available vaccines. The NDCs from the prescription drug events (PDE) file that will be used to identify RZV exposure as a prescription dispensing in an outpatient pharmacy setting are: 58 160-0828-01; 58 160-0829-01; 58 160 082 311; 58 160-0828-03; 58 160-0829-03; 58 160 082 311; and 58 160-0823-11. The CPT code 90750 for RZV will identify vaccine administration in a Part B (physician office setting) claim. It is anticipated that most will be identified from the PDE file and should only occur in one of the claims files since Medicare will not pay for the same vaccine administration twice, i.e., exposure will not be counted twice.

RZV vaccination records occurring within 27 days after a previous RZV vaccination record (i.e., on days 1-27, where the day of the previous RZV record is day 0) will be considered a duplicate record and will be deleted. The *participant* will be retained for the analytic cohort. For *participants* who receive more than two doses of RZV, even after removal of possible duplicates, we will exclude from analysis RZV doses beyond two per study *participant*.

Preventive care visits for comparison with RZV vaccinations will be identified by means of CPT, ICD-10, and Healthcare Common Procedure Coding System (HCPCS) codes, as shown in Table 2. The presence of any of the below codes qualifies as an eligible "preventive care visit."

Table 2Preventive care visit description for the comparators in the cohort analyses

ICD10	HCPS	CPT	Code Description
			Routine Adult Annual Exam
		99386	Initial comprehensive preventive medicine evaluation and management of an individual including an age and gender appropriate history, examination, counseling/anticipatory guidance/risk factor reduction interventions, and the ordering of laboratory/diagnostic procedures, new patient; 40-64 years
		99387	Initial comprehensive preventive medicine evaluation and management of an individual including an age and gender appropriate history, examination, counseling/anticipatory guidance/risk factor reduction interventions, and the ordering of laboratory/diagnostic procedures, new patient; 65 years and older

Z13.820			Encounter screening for osteoporosis

9.3.2. Outcome identification algorithms

The primary HOIs are GBS, gout, PMR, and GCA. Secondary HOIs are SVT and ION. Table 3 describes the case definition algorithm for the primary and secondary HOIs, which also details the sensitivity analyses where validated outcome identification algorithms are not available in the literature for reference.

- All algorithms use medical claims from the inpatient, outpatient or carrier claim files and are based on the ICD-10 codes.
- An inpatient claim is defined as a claim generated from an admission to a hospital.
- An ED (Emergency Department) visit is defined as a claim generated from a visit to an urgent care unit within a hospital, but it is not a hospital admission.
- An outpatient claim is defined as a claim generated by a visit to a provider in an ambulatory practice setting, e.g., physician office, health clinic.
- For algorithms that require ≥ 2 claims, the date of the first claim will define the first occurrence of the HOI. The two claims must occur within the designated follow-up interval.
- For the SCRI design, new onset of the HOI, i.e., incident case, is determined based on the first occurrence and no record of the HOI in the preceding 365 days.
- For the cohort design, new onset of the HOI, i.e., incident case, is determined based on the first occurrence after the index date (i.e., RZV vaccination or the preventive care visit date for RZV unvaccinated comparators) and no record of the HOI in the 365 days preceding the index date (i.e., baseline period).
- For GBS, the earliest onset date is the hospitalization date for claims in the inpatient setting or the earlier GBS claim when the diagnosis occurs in any setting followed by an inpatient claim within 7 days.

Table 3HOI case identification algorithms

1	2	3	4	5	6	7	8	9	10
Study Outcome (Study design)	ICD-10 code(s) for case ascertainment	Validation Statistics	Other requirements ^c	Setting for case ascertainment	Risk Interval	Look-back period & settings to determine incidence	What to look back for	What to look back from	Sensitivity Analysis
GBS (SCRI)	G61.0	PPV: 50% (Inpatient visit) ¹⁴	None	Inpatient primary position OR Diagnosis in any setting followed by an inpatient claim within 7 days	Days 1-42	1 year; inpatient; primary position only	Same as in Col.2	HOI	N/A
Gout (SCRI)	M10.x, M1A.x (chronic gout)	PPV: 61% (≥ 2 visits associated with the diagnosis) ¹⁵	At least one gout- specific oral medication (allopurinol, colchicine, probenecid, febuxostat) prescribed within 3 months after the first date of the diagnosis.	≥2 outpatient claims within the follow-up windowa OR ≥1 inpatient claim	Days 1-30	1 year; diagnosis code –all settings ^b OR At least one gout- specific oral medication (allopurinol, colchicine, probenecid, febuxostat);	Same as in Col. 2 OR Col. 4	HOI	-Exclude chronic and secondary gout codes. -Examine frequency distribution of ICD-10 codes and consider low- frequency codes such as codes for chronic gout (M1A*), lead- induced gout (M10.1*, drug-induced gout (M10.2*), and gout due to renal impairment (M10.3*) (note: this exclusion of gout codes does not apply in assessing prevalent gout) ^d

209696 (EPI-ZOSTER-032 VS US DB) Protocol Amendment 3 Final

1	2	3	4	5	6	7	8	9	10
Study Outcome (Study design)	ICD-10 code(s) for case ascertainment	Validation Statistics	Other requirements ^c	Setting for case ascertainment	Risk Interval	Look-back period & settings to determine incidence	What to look back for	What to look back from	Sensitivity Analysis
PMR (Cohort)	M35.3 – PMR M31.5 – GCA w/ PMR	Sensitivity: 99.5% Specificity: 92.2% ¹⁶ (based on the 3 methods used by Bernatsky: diagnosis in inpatient or outpatient, or a visit by a rheumatologist/ internist)	2 oral glucocorticoids (cortisone, dexamethasone, hydrocortisone, methylprednisolone, prednisolone, prednisone) prescriptions; The first dispensing within 6 months of PMR diagnosis and the second dispensing date within 6 months after the first dispensing.	≥2 outpatient claims within the follow up window a OR ≥1 inpatient claim	Days 1-183	1 year; all settings⁵	Same as in Col. 2	Exposure	N/A
GCA (Cohort)	M31.6 (GCA), M31.5 (GCA with PMR), M31.9 (necrotizing vasculopathy unspecified)	Not available	2 oral glucocorticoids (cortisone, dexamethasone, hydrocortisone, methylprednisolone, prednisolone, prednisone). The first dispensing within 6 months of GCA diagnosis and the second dispensing date within 6 months after the first dispensing.	≥2 outpatient claims within the follow up windowª OR ≥1 inpatient claim	Days 1-183	1 year; all settings⁵	Same as in Col. 2	Exposure	-Use the primary algorithm based on the GCA diagnosis code and steroid prescription but ADD a requirement for a temporal artery biopsy at the time of diagnosis, as determined by a CPT code=37609

209696 (EPI-ZOSTER-032 VS US DB)

Protocol Amendment 3 Final

1	2	3	4	5	6	7	8	9	10
Study Outcome (Study design)	ICD-10 code(s) for case ascertainment	Validation Statistics	Other requirements ^c	Setting for case ascertainment	Risk Interval	Look-back period & settings to determine incidence	What to look back for	What to look back from	Sensitivity Analysis
ION (Cohort)	H47.01	Not available	Exclude patients who had coronary artery bypass graft (CABG) surgery ¹⁷ or lumbar or lumbosacral spinal fusion and/or laminectomy surgery within 30 days before ION diagnosis date	≥1 claim in all settings	Days 1-183	1 year; all settings ^b ICD code only	Same as in Col. 2	Exposure	Additional criteria for arteritic: ≥ 40 mg/day of prednisone prescription ± 4 weeks of the diagnosis plus an ophthalmologist/neuro- ophthalmologist consult (if possible) and GCA diagnosis within 3 months; lookback to rule out prevalent cases will use ICD code only; all settings
SVT (SCRI)	147.1	Sensitivity-91.7% ¹⁸	None	≥1 ED or inpatient claim any position	Days 1-30	1 year; all settings ^b any position	Same as in Col. 2	HOI	N/A

Definitions: ALS - Amyotrophic Lateral Sclerosis; CVA - Cerebrovascular Accident; GCA - Giant Cell Arteritis; GSB - Guillain-Barré Syndrome; ION - Ischemic Optic Neuropathy; PMR - Polymyalgia Rheumatica; SCRI - Self-controlled Risk Interval; SVT - Supraventricular Tachycardia;

^a Outpatient visits are defined using ≥2 claims for consistency with methods used by CMS algorithms using the CMS CCW Medicare data to define chronic conditions, and to avoid misclassification of the outcome due to the potential for 1 visit to reflect rule-out diagnosis.

^b Includes inpatient, emergency department, and outpatient settings.

^c Based on external expert opinion.

^d Consistent with the study EPI-ZOSTER-030 VS US DB, no analysis will be conducted for the gout sensitivity HOI definitions. These definitions are for administrative purposes only .

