9.4. Data sources

9.4.1. Description of the databases (Amended 15 July 2022)

CMS CCW Medicare data is a secondary administrative database of all paid claims for fee-for-service billable healthcare services in inpatient and outpatient settings, SNF, hospice, home health services, and for the provision of DME and prescription drugs for older and disabled US citizens. The claims data are available in six different datasets and a unique identification (ID) is used to link an individual across all data sets. Annex 1 provides a detailed description of the data sets and the variables within each dataset.

Master Beneficiary Summary File (MBSF): The information in this dataset relevant to this study includes beneficiary enrollment *each calendar month* in Medicare Parts A, B, and D. This file will be used to obtain information on the baseline study variables, including original and current enrollment reason, eligibility, and demographic characteristics.

Inpatient Claim File: This dataset contains fee-for-service claims submitted by inpatient hospital providers for reimbursement of facility costs, including hospitalizations and ED visits. Up to 25 diagnosis fields, including the admission diagnosis as well as a principal diagnosis, are available on each claim. CPT codes for services rendered are available on each claim.

Outpatient Claim File: This dataset contains fee-for-service claims submitted by *institutional outpatient providers*. Institutional outpatient providers include hospital outpatient departments, rural health clinics, renal dialysis facilities, outpatient rehabilitation facilities, comprehensive outpatient rehabilitation facilities, Federally Qualified Health Centers and community mental health centers. The outpatient files contain up to 25 diagnosis fields as well as CPT codes.

Carrier File: This dataset includes fee-for-service claims submitted by *professional providers*, including physicians, physician assistants, clinical social workers, nurse practitioners and by *organizational providers*, including freestanding facilities (i.e., independent clinical laboratories), ambulance providers, freestanding ambulatory surgical centers and freestanding radiology centers. The Carrier files contain up to 12 diagnosis fields as well as CPT codes.

SNF Claim File: This dataset includes fee-for-service claims for paid services that are submitted by SNF *institutional facility providers*.

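### Gout: an emergency-department claim cannot qualify or date a case but does count in the look-back, so a first attack coded in the ED can be excluded by its own claim

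*Combined protocol and SAP*

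**What the plan says.** Section 9.3.2 separates three settings:

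- Inpatient: "An inpatient claim is defined as a claim generated from an admission to a hospital".
- ED: a category of its own, tied to a hospital urgent care visit that does not count as an admission.
- Outpatient: "An outpatient claim is defined as a claim generated by a visit to a provider in an ambulatory practice setting, e.g., physician office, health clinic".

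The gout row of Table 3 qualifies a case on "≥2 outpatient claims within the follow-up windowa OR ≥1 inpatient claim" (the trailing letter is footnote mark a), plus a gout-specific oral drug within three months after the first diagnosis date. Where two claims are needed, the first of them dates the outcome.

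For the self-controlled risk interval (SCRI) design, a case is new-onset only if the 365 days before the outcome date are clear. For gout the look-back searches diagnosis codes in all settings, or any of the listed gout drugs. Footnote b defines all settings: "Includes inpatient, emergency department, and outpatient settings".

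Section 9.4.1 describes the Inpatient Claim File as holding claims "for reimbursement of facility costs, including hospitalizations and ED visits".

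**The concern.** For gout, the set of claims that can disqualify a patient is wider than the set that can qualify or date one, and the ED falls in the difference. Because the look-back runs from the outcome date and not from vaccination, claims from the same episode fall inside it. An ED visit shortly before the first qualifying claim is then treated as evidence of old disease when it is the onset of the new one.

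Gout is a primary outcome, and its 30-day window is aimed at acute attacks, some of which will be coded first in an ED. Little else in the plan would reveal the problem. There is no chart review (9.4.2, 9.9). Footnote d of Table 3 says no analysis will be run on the alternative gout definitions. The quality control in 9.8 checks output against the protocol, which gives ED claims no role in gout ascertainment.

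**Working it through.** **1. Applying the rules.** Inputs are the 9.3.2 definitions, the gout row of Table 3, the first-claim dating rule and the 365-day look-back. The drug requirement is assumed met, and there is no gout record before day 5. Days count from vaccination.

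| Gout claims | Literal 9.3.2 and Table 3 | With the fix below |
|---|---|---|
| ED day 5 only | not a case | not a case |
| ED day 5, office day 12 | not a case | new onset, day 5 |
| ED day 5, office days 12 and 20 | dated day 12, excluded by the ED code | new onset, day 5 |
| ED day 5, admission day 8 | dated day 8, excluded by the ED code | new onset, day 5 |
| ED day 5, admission day 5 | new onset, day 5 | new onset, day 5 |
| Office days 5 and 12 | new onset, day 5 | new onset, day 5 |

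In the third and fourth rows, a gout drug filled between day 5 and the dated onset would exclude the patient even if the ED code were ignored. Relabelling ED claims as outpatient would not be enough: the fourth row would still be dated day 8 and excluded. The dating rule has to change as well.

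**2. The plan's event target.** Section 9.7.1.1 requires 68 gout cases for 80% power at a relative risk (RR) of 2, two-sided alpha 0.05. The signed-root likelihood-ratio formula for self-controlled case series is n = (z_a + z_b√B)²/A. Equal 30-day windows give r = 0.5.

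- A = 2[(2/3)ln 2 − ln 1.5] = 0.1133
- B = (ln 2)²/A × (2 × 0.25)/1.5² = 0.943
- n = (1.960 + 0.842 × 0.971)²/0.1133 = 68.1

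The plan's 68 is reproduced.

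**3. Cases to be expected.** Section 9.2.2 projects a little more than 2 million eligible vaccinees. Section 9.5.2 gives a gout rate of 200 per 100 000 person-years.

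- Per 100 000 control windows: 200 × 30/365.25 = 16.43. Table 4 prints 8.71, so both are carried.
- Control-window cases, one dose each: 2 000 000 × 16.43/100 000 = 329 (174 with the printed figure).
- Total at RR 2, three times that: 986 (522).
- Share that would have to be lost to reach 68: 1 − 68/986 = 93% (1 − 68/522 = 87%).

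**4. Effect on the estimate.** Let f be the share of background cases lost by the ED route and f_e the share lost among vaccine-related cases. At a true RR of 2 the expected incidence rate ratio (IRR) is [(1 − f) + (1 − f_e)]/(1 − f).

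- If f_e = f, the IRR is 2 and the standard error rises by 1/√(1 − f). The documents give no value for f. Assuming 5% to 20%, the rise is 3% to 12%.
- If f_e is larger than f, the IRR is attenuated. Purely as illustration, f_e of 1.5 to 2 times f gives 1.97 (f = 0.05, f_e = 0.075) down to 1.75 (f = 0.20, f_e = 0.40). Nothing in the documents supports either assumption.

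**The case against.** **Power.** A reader might take 68 as the cases available, subtract an ED share and infer that power falls below 80%. The documents do not support this. Section 9.7.1.1 sets 68 as the minimum recorded, counted after the algorithm has been applied, and the projected population yields several times that number.

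**Single ED claim.** A reader might also infer from 9.4.1 that one ED claim would pass as the single inpatient claim. Section 9.4.1 describes what a file contains, whereas 9.3.2 defines the claim type by admission. The supraventricular tachycardia (SVT) row names ED and inpatient separately, which would be redundant if one included the other. The gout drug would still be required. Section 9.3.4 uses place of service and revenue code to designate setting. It says so for covariates, but it shows that setting need not be read from the file. What remains is a programming risk that one sentence removes.

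**Breadth.** Disqualification needs a later admission or two later office claims. A same-day admission remains incident, and an ED claim alone or with one office claim is simply not a case. It would therefore be wrong to say that ED presentations can never become cases. Nor is gout alone in having a look-back wider than its ascertainment: SVT has that too, although it accepts ED claims.

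**Self-control.** The same rule applies in both windows, so a loss shared equally cancels from the IRR. This stands.

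**Other outcomes.** Polymyalgia rheumatica (PMR) and giant cell arteritis (GCA) look back from exposure, so an ED claim after the index date disqualifies no one.

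None of this removes the narrow fault. Under the stated gout rules, a new attack can be classified as prevalent because of its own ED code. Footnote a justifies requiring two outpatient claims; it gives no reason for leaving ED claims out. The Guillain-Barré (GBS) rule shows that the plan can bridge settings: a diagnosis anywhere followed by an inpatient claim within seven days is accepted, and the date of that diagnosis sets onset.

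**Conclusion.** The point holds for gout. It is a stated rule that misclassifies some new-onset cases of a primary outcome, and more than missing detail. The consequence is fewer cases and some loss of precision. Attenuation follows only if vaccine-related attacks reach the ED more often than background attacks, which the documents do not address. The size is unknown because no ED share is given. Power is not at risk on the plan's own projections, although the 200 per 100 000 rate is not said to have been measured with the Table 3 algorithm. The change is worth making because it is cheap and keeps true incident cases with the right onset date.

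**What to change.** For gout, in Table 3 and 9.3.2:

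1. Count an ED claim without admission as one of the two required non-inpatient claims.
2. Let the first gout claim of the qualifying episode, in any setting, set the outcome date. State how far apart claims of one episode may lie.
3. Run both the diagnosis and the drug look-back over the 365 days before that date.
4. State that an ED visit without admission is never the single inpatient claim, whichever file holds it, since 9.4.1 places ED visits in the inpatient file.

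SVT and GBS need no change on this point. PMR and GCA need at most a note on how ED claims are treated, for consistency.

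The cost is a slightly wider gout case definition, because an ED claim plus one office claim would now qualify, and minor programming to separate ED visits from admissions.

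### For gout, PMR and GCA, two same-day claims from one visit can satisfy the two-outpatient-claim rule, leaving only the drug criterion to separate a rule-out visit from a case

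*Combined protocol and SAP*

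**What the plan says.** Section 9.3.2 and Table 3 define gout, PMR and GCA, three of the four primary outcomes, by at least one inpatient claim or at least two outpatient claims. Two conditions govern the pair: "For algorithms that require ≥ 2 claims, the date of the first claim will define the first occurrence of the HOI", and "The two claims must occur within the designated follow-up interval".

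On where claims are sought: "All algorithms use medical claims from the inpatient, outpatient or carrier claim files and are based on the ICD-10 codes". An outpatient claim is described thus: "An outpatient claim is defined as a claim generated by a visit to a provider in an ambulatory practice setting, e.g., physician office, health clinic". Section 9.4.1 describes the two non-inpatient sources. For the Outpatient file, "Institutional outpatient providers include hospital outpatient departments, rural health clinics, renal dialysis facilities" and others; for the Carrier file, "This dataset includes fee-for-service claims submitted by *professional providers*, including physicians" and other clinicians.

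Footnote a to Table 3 gives two reasons for asking for two claims: consistency with the CMS chronic-condition algorithms, and "to avoid misclassification of the outcome due to the potential for 1 visit to reflect rule-out diagnosis". The positive predictive value of 61% cited for gout is for "≥ 2 visits associated with the diagnosis".

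Column 4 of Table 3 adds a drug criterion. Gout needs at least one gout-specific oral drug within 3 months after first diagnosis. PMR and GCA need two oral glucocorticoid prescriptions, the first within 6 months of diagnosis and the second within 6 months after the first.

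**The concern.** The operative rule counts claims, while its stated purpose and the gout validation figure both count visits. If one visit to a hospital outpatient department leaves a facility claim and a clinician claim with the same code on the same day, it meets the two-claim rule. A single visit to a private office, which leaves one carrier claim, does not. Two patients with the same clinical history could then be classified differently because of where they were seen.

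Little downstream would show this. Sections 9.4.2 and 9.9 rule out chart review. PMR has no alternative definition. Footnote d says that the alternative gout definitions will not be analysed. GCA has a stricter biopsy-based definition, but section 9.7.6 carries it to inference only if case numbers allow.

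At stake is the specificity of three primary case definitions. False positives unrelated to vaccination pull the incidence rate ratio or hazard ratio toward 1, which in a safety study is the unfavourable direction.

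**Working it through.** **1. Does the text exclude same-day pairs?**

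| Element | What it counts or requires |
|---|---|
| Table 3, setting column | at least two outpatient *claims* |
| 9.3.2, dating rule | the earliest claim sets the onset date |
| 9.3.2, timing rule | both claims in the follow-up interval; a same-day pair complies |
| 9.3.2, files | institutional outpatient and carrier both searched |
| Table 3, footnote a | protection against a single *visit* |
| Table 3, gout PPV | at least two *visits* |

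No passage asks for distinct dates, a minimum gap, or collapsing of same-day claims across files. Followed literally, two same-day claims meet the count.

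**2. What does the drug criterion then remove?** A suspected case that is never treated is removed for all three outcomes. For gout the drugs are gout-specific, and Column 7 removes anyone with a gout code or gout drug in the prior year, so protection is fairly strong. For PMR and GCA any two oral glucocorticoid prescriptions with the stated timing suffice, whatever the indication. One fill is not enough, but a patient with two fills for another condition passes.

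**3. The plan's sample-size figures.**
- Gout, equal windows, RR 2, 80% power, by the signed-root likelihood method: p = 2/3; A = 2[p·ln 2 − ln 1.5] = 0.113; B = (ln 2)²·p(1−p)/A = 0.943; events = (1.96 + 0.842·√B)²/A = 68.1. Table 4 has 68.
- PMR, Poisson regression, 20% exposed, half a year of follow-up, b = 0.000405: N = [1.96·√(1/(0.2·0.8)) + 0.842·√(1/0.8 + 1/(0.2·2))]² / (0.5·b·(ln 2)²) = 438 239, as in Table 5. The same formula with b = 0.000092 and RR 3 gives GCA's 723 362.

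**4. Illustrative dilution.** Assume a share f of background cases are false positives unrelated to vaccination. Then observed RR = RR(1−f) + f. The documents give no value of f.

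| f | True RR 2 seen as | True RR 3 seen as | Gout events needed | Power at 68 events |
|---|---|---|---|---|
| 0 | 2.0 | 3.0 | 68 | 80% |
| 5% | 1.95 | 2.9 | 73 | 77% |
| 10% | 1.9 | 2.8 | 79 | 74% |
| 20% | 1.8 | 2.6 | 94 | 66% |
| 30% | 1.7 | 2.4 | 114 | 58% |

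**5. What would a distinct-date rule do to true cases?** Assume onset uniform over the window and an exponential time to the second visit with mean m of 14 to 30 days (an assumption, not in the documents).
- Gout, both claims within one 30-day window: share lost = (m/30)(1 − e^(−30/m)) = 41% at m = 14 and 63% at m = 30.
- Gout, both claims within days 1-60: risk-window capture = 1 − (m/30)(e^(−30/m) − e^(−60/m)) = 95% or 77%; control-window capture = 59% or 37%. The ratio is 1.6 or 2.1 with no vaccine effect.
- PMR and GCA, 183 days: share lost = (m/183)(1 − e^(−183/m)) = 8% or 16%, much the same in both arms because each has the same nominal 183-day period.

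These losses apply to cases that rely on the outpatient route. Under the present rule, different-day pairs already carry the gout problem; a distinct-date rule extends it to every outpatient pair.

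**The case against.** - **Two claims are not yet a case.** A reader might infer that any rule-out visit billed twice becomes a case. The documents do not support that, because the drug criterion is mandatory. This stands, and it limits the concern mainly to PMR and GCA.
- **Double billing is inferred.** Section 9.4.1 says who submits to each file. It does not say that one visit yields a claim in both, and it would not hold for every office visit. Footnote a shows that more than one visit was intended, and it appeals to CMS algorithms whose specifications lie outside these documents. This also stands, but an intention in a footnote does not bind a programmer who follows the rule as written.
- **Dilution would not leave the study short of power.** At the plan's 200 per 100 000 person-years, a 30-day window gives 200 × 30/365.25 = 16.4 gout cases per 100 000 doses. Two million vaccinees with two doses each give about 657 per window, far above 114. At f = 30%, detecting the diluted ratio takes 769 293 people for PMR and 1 175 059 for GCA. One fifth of these is about 154 000 and 235 000 vaccinees, against just over 2 million expected in section 9.2.2. This is correct: what suffers is the estimate and its meaning, not the plan's ability to test.
- **A false harm signal.** Section 7 notes higher reactogenicity on days 0-6, so a reader might infer that reaction visits coded as gout or PMR would create a spurious signal. The documents give no rate for such visits. Each would also have to be doubly billed and treated, and a reaction worked up over two visits would pass a distinct-date rule anyway. No probability of a false signal can be supported.
- **The obvious remedy can do harm in gout.** Step 5 of the working bears this out, and the fix has to allow for it.

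**Conclusion.** The point holds in a limited form. As written, the outpatient rule for gout, PMR and GCA can be met by two same-day claims from one visit, against the purpose given in footnote a and the two-visit basis of the gout predictive value. The drug criterion is then the only remaining barrier: fairly strong for gout, weak for PMR and GCA.

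That the text lacks a distinct-date condition is certain. That one visit can appear in both files is an inference from the file descriptions. The number of cases affected is unknown, so the dilution figures (2 seen as 1.9 or 1.7; 3 seen as 2.8 or 2.4, at f of 10% or 30%) show direction and scale only. They also assume that the false positives are unrelated to exposure. The documents do not support a claim that the primary conclusions would be reversed.

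**What to change.** In section 9.3.2 and Table 3:

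1. **PMR and GCA:** require two outpatient claims with the diagnosis on different service dates, and count same-day facility and professional claims as one.
2. **Gout:** apply the same rule only together with a fixed period after the earliest claim in which the second may fall, identical for risk-window and control-window cases, with onset still dated at the earliest claim. The period may run past the control interval, so the enrollment requirement in section 9.7.6 has to cover it. If the sponsor does not want this, run the distinct-date rule for gout as a sensitivity analysis.
3. **All three outcomes:** report the number of cases that qualified only on same-day claims, by window or by arm.

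The cost is a few lines of text, a date condition in the case-finding code, and one count per outcome. The downside is the loss of some true cases without a timely second visit: under the revisit times assumed above, about 8 to 16% of outpatient-route PMR and GCA cases, mostly late in follow-up. For gout the loss depends on the length of the confirmation period, but it would no longer differ by window. The change should be made before the case-finding code is fixed.
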